Some nutritional status indicators available for determination at the Oncology Clinic were assessed - body mass index (weight measurements were carried out before surgery, on the 5th, 10th and 15th days), basal metabolic rate (calculated using the Harris-Benedict equation, based on anthropometric data of the patient (gender, age, weight and height).), laboratory parameters: blood hemoglobin, lymphocytes, total protein, serum albumin, serum transferrin, total bilirubin and direct, ALT, AST, which are related to the traditional method for assessing nutritional status.

Additionally, we assessed the duration of postoperative gastostasis, the timing of the onset of intestinal motility, the appearance of stool, the return to a normal diet, the length of patients' stay in the ICU, the readmission of patients to the ICU and the duration of the postoperative bed-day, and the incidence of complications was calculated.

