### Clinical research program:

The study was carried out on the basis of the KGP at the RVC "Multidisciplinary Hospital No. 3 of the city of Karaganda". Venue: intensive care unit.

To identify nutritional deficiency, there are screening methods recommended by the international clinical nutrition associations ASPEN (American Society for Parenteral and Enteral Nutrition - ASPEN) and ESPEN (European Society for Parenteral and Enteral Nutrition - ESPEN), including questioning patients, using standard anthropometric and laboratory data, which makes it possible to assess nutritional status and the degree of its impairment.

At the first stage, the clinical condition of the patient was assessed using the Nutritional Risk Screening (NRS, 2002), Subjective Global Assessment (SGA) and Nutritional Risk Index (NRI) protocols before surgery and on the 5th, 10th, 15th day after surgery .

A comparative assessment of the clinical effectiveness of the use of types of nutritional nutrition in a complex of therapeutic measures after these operations in the hepatopancreatoduodenal zone was carried out.

Some nutritional status indicators available for determination at the Oncology Clinic were assessed - body mass index (weight measurements were carried out before surgery, on the **5th, 10th and 15th** days), basal metabolic rate (calculated using the Harris-Benedict equation, based on anthropometric data of the patient (gender, age, weight and height).), laboratory parameters: blood hemoglobin, lymphocytes, total protein, serum albumin, serum transferrin, total bilirubin and direct, ALT, AST, which are related to the traditional method for assessing nutritional status.

Additionally, we assessed the duration of postoperative gastrostasis, the timing of the onset of intestinal motility, the appearance of stool, the return to a normal diet, the duration of patients' stay in the ICU, the repeated admission of patients to the ICU and the duration of the postoperative bed-day, and the incidence of complications was calculated.

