As can be seen from the presented data, in the preoperative period, according to the SGA assessment, 24 patients in the enteral group, 19 patients in the parenteral group, and 17 patients in the mixed group had normal nutritional status before surgery, with variations relative to patients with moderate to severe malnutrition. Assessment of nutritional status before surgery using the NRI scale allowed us to confirm the nutritional status of the vast majority of patients in all groups as relatively normal

Thus, in 62 of the 91 patients examined, the NRI was assessed as true negative (normal nutritional status), in 26 as true positive (moderate malnutrition), and in 3 as severe malnutrition. Data from the NRI method during this time period had a strong correlation with the results of the SGA scale ( $p < 0.005$ ).

On the 10-12th day of the postoperative period in patients of the “enteral” group, the results of the assessment on the SGA scale remained unchanged; according to the NRI rating scale, there was an increase in “moderate malnutrition” per patient (25%).

With parenteral nutritional support, 17 patients had “normal nutrition”, 14 patients had moderate malnutrition, with regression of “severe malnutrition” in 1 patient. In the mixed nutrition group, there was a complete elimination of signs of “severe malnutrition” by 100% according to the given scales ( $p < 0.005$ ).

In patients of all study groups, throughout the entire period of nutritional support, fluctuations in the level of basal metabolism were observed in average values of  $335.89 \pm 53.6$  kcal/day (13.44%) from the initial value - 1-2 days of the postoperative period and were due to variability body mass index and the dynamics of the temperature curve after surgery.

In patients in the groups with enteral and parenteral nutrition, by the end of these types of energy subsidies (days 10-15), the level of basal metabolism was observed to approach its initial values -  $2500.1 \pm 353.4$  kcal/day and  $2350.0 \pm 330.5$  kcal/day days accordingly. With a mixed type of nutrition, there was a statistically significant decrease in the level of basal metabolism by 6.78% ( $2250.0 \pm 105.2$  kcal/s), which allows us to conclude that patients' energy costs are more effectively covered with this option of nutritional support in a comparative aspect with isolated types nutrition ( $p < 0.03$ ).

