This fact was obviously associated with the preservation/restoration of parietal digestion in the gastrointestinal tract in the early postoperative period, despite postoperative intestinal paresis of varying degrees, and the involvement of nutrients in anabolic processes with parallel “covering” of the required daily caloric intake by parenteral administration of mixtures.

Evaluation and subsequent analysis of the results of laboratory examination in groups of patients in a comparative aspect showed a relatively slow and gradual decrease in the level of total blood protein by the 5th day of the postoperative period, on average, by  $6.8 \pm 0.95\%$  of the initial values, which,

apparently, was due to increased catabolism and ongoing protein losses (exudation, drainage, etc.) with a fairly significant increase by the end of nutritional support.

Thus, a statistically significant increase in the level of total blood protein was noted in the mixed nutrition group ( $p = 0.004$ ). In the groups with enteral and parenteral nutrition, differences in the dynamics of total protein levels were found at the level of a statistical trend:  $p=0.108$  and  $p=0.129$ , respectively.

When analyzing changes in the number of blood lymphocytes, it should be noted that before the operation the relative value of lymphocytes in the groups was significantly reduced ( $25.9\pm3.7\%$ ), but taking into account the methods and volumes of the operation, the tension of the cellular and humoral parts of the immune system, the dynamics of their level was expressed in the form of a statistically significant increase in the level of lymphocytes in the postoperative period by 10-12 days.

Thus, there was a steady increase in the level of blood lymphocytes by the 10th day of the postoperative period in all groups, on average by 8.95% ( $p = 0.000$ ), by 10.35% ( $p = 0.003$ ), by 10.91% ( $p = 0.000$ ) respectively.

This dynamics reflects the positive effect on the immune status of patients of the combined use of parenteral and enteral types of nutritional support in the postoperative period in this group of patients.

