### **Conclusion:**

1. According to the NRI nutritional status assessment scales, the SGA mixed type of nutritional support at the time of transfer of patients to the specialized department and upon completion of this area of intensive therapy in the specialized department by 12-15 days of the postoperative period showed higher effectiveness in stabilizing the condition and maintaining the patients' caloric intake in a comparative aspect with the group of isolated enteral nutrition and parenteral nutrition.
2. Throughout the entire period of isolated enteral, parenteral and mixed nutritional support, all patients (100%) showed a relatively constant level of total blood protein.
3. In patients of all three groups, throughout the entire period of nutritional support, fluctuations in the level of basal metabolism were observed, which was due to the variability of body mass index and the dynamics of the temperature curve after surgery. In patients in the groups with enteral and parenteral nutrition, by the end of nutritional support (days 15-20), the level of basal metabolism was observed to approach its initial values. With a mixed type of nutrition, a statistically significant decrease in the level of basal metabolic rate was observed, which suggests a more effective coverage of the energy costs of patients with this option of replenishing nutritional ingredients.

**Researcher:** [name], PhD student KSMU

[contact].

e-mail: [contact].

[figure not shown]
Signature  17.03.2020

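### A fall in a calculated basal metabolic rate cannot show that mixed nutrition covered patients' energy costs better

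*Combined protocol and SAP*

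**What the plan says.** Protocol section III.1 (Methods and procedures) lists "basal metabolic rate (calculated using the Harris-Benedict equation, based on anthropometric data of the patient (gender, age, weight and height" among the nutritional indicators. The report's clinical research program says the same: "calculated using the Harris-Benedict equation, based on anthropometric data of the patient". Weighing was planned before surgery and on days 5, 10 and 15. Research objective 3, in both protocol and report, judges effectiveness on two things: nutritional status and the course of basal metabolism.

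The report's Results and discussion text states:

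- Across all groups the rate fluctuated by 335.89 ± 53.6 kcal/day (13.44% of the initial value), and this was "due to variability body mass index and the dynamics of the temperature curve after surgery".
- For the enteral and parenteral groups, "by the end of these types of energy subsidies (days 10-15), the level of basal metabolism was observed to approach its initial values", with 2500.1 ± 353.4 and 2350.0 ± 330.5 kcal/day.
- "With a mixed type of nutrition, there was a statistically significant decrease in the level of basal metabolism by 6.78" per cent, to 2250.0 ± 105.2 (unit printed as kcal/s, read here as kcal/day), with p<0.03.
- From this fall the report concludes that "energy costs are more effectively covered with this option of nutritional support in a comparative aspect with isolated types nutrition".
- The explanation offered is gut digestion together with the covering "of the required daily caloric intake by parenteral administration of mixtures".

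Conclusion 3 restates the finding: "a statistically significant decrease in the level of basal metabolic rate was observed, which suggests a more effective coverage of the energy costs".

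**The concern.** Coverage of energy costs compares energy delivered with energy required or spent. The variable used is an estimate of requirement from body size. It has no delivered-energy term and no measured-expenditure term. The protocol's study plan, section III.1 and the report's clinical research program name no delivered-energy variable. Blood gases and nitrogen metabolism are listed, but neither is described as a measure of expenditure or used for this claim.

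The direction is also a problem. As defined, a fall means lower weight, and the protocol's introduction cites work linking a 5% in-hospital weight loss to a doubled stay and 3.3 times the complications. A reader could therefore take a possible warning sign for a benefit.

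Energy coverage is the only comparative claim in Conclusion 3 and one of the statements favouring mixed nutrition.

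**Working it through.** **1. What the variable can register.** Inputs, from section III.1: sex, age, height, weight. Sex and height are fixed, and age is effectively fixed over 15 days. So a change in the calculated rate is a change in weight. Write coverage as E/R, with E the energy delivered and R the requirement. Only R is available. If E stayed constant while R fell by 6.78%, E/R would rise by a factor of 1/(1 − 0.0678) = 1.073 without one extra kilocalorie being delivered. The fall in R therefore says nothing about E.

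**2. The 6.78% figure.** It cannot be reproduced, because the available text prints no mixed-group starting value. If it is relative to the group's own start:

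- implied baseline = 2250.0/(1 − 0.0678) = 2413.6 kcal/day
- implied fall = 2413.6 − 2250.0 = 163.6 kcal/day

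It does not match the other printed values either: 2250.0 is 10.0% below 2500.1 and 4.3% below 2350.0.

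**3. What it would mean in weight (illustration only).** Assume no added factor, and that weight supplies a share s of the calculated rate, with s between 0.5 and 1.0. This range is an assumption, not a figure from the documents. Relative weight fall = 6.78%/s:

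- s = 1.0: 6.8%
- s = 0.7: 9.7%
- s = 0.5: 13.6%

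No weights are printed, and early change may include fluid or resected tissue.

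**4. Initial or end values?** 335.89/2500.1 = 13.44%, which fits 2500.1 as an initial value. But suppose 2500.1 and 2350.0 are both initial and the mixed start was 2413.6. The all-group start is then (31 × 2500.1 + 30 × 2350.0 + 30 × 2413.6)/91 = 2422.1, and 335.89/2422.1 = 13.87%, not 13.44% (unless 13.44% averages individual percentages). The text does not settle it.

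**5. If they are end values, does p<0.03 fit a between-group comparison?** The statistical methods section lists both the error of the mean and the standard deviation, so ± can be either. Welch t-tests with n = 31, 30 and 30:

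| Comparison | ± read as | Difference, kcal/day (95% CI) | t | p |
|---|---|---|---|---|
| Enteral − mixed | SD | 250 (116 to 385) | 3.77 | 0.0006 |
| Parenteral − mixed | SD | 100 (−29 to 229) | 1.58 | 0.12 |
| Enteral − mixed | SE | 250 (−498 to 998) | 0.68 | 0.50 |
| Parenteral − mixed | SE | 100 (−604 to 804) | 0.29 | 0.77 |

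The SE reading implies SDs of 353.4√31 = 1968, 330.5√30 = 1810 and 105.2√30 = 576 kcal/day. These look implausible, but the text does not exclude them. On neither reading do the end values show a difference from parenteral nutrition. None of these tests examines a within-group change or compares changes between groups, so p<0.03 cannot be assigned to a comparison.

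**6. Temperature.** The results and Conclusion 3 cite the temperature curve, which is not an input to the stated calculation. Either that explanation is wrong, or an unreported factor was used and both method sections misdescribe the variable. With such a factor, the fall could reflect less fever or lower weight. It would still contain no delivered energy.

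**The case against.** The strongest reply is that an unreported temperature or stress factor was probably applied, since the report itself cites temperature. The fall might then partly reflect settling fever, and the comparison with a 5% weight loss would not apply. The report also says that severe malnutrition disappeared in this group, which sits badly with large weight loss. This limits the weight illustration, which holds only for the formula as stated. It does not help the inference: an adjusted requirement is still a requirement.

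On scope, Conclusion 3 is hedged, basal metabolism is not named as a primary outcome, and only one component of Objective 3 is affected. That is correct, and the point is confined accordingly. It is still a formal conclusion favouring one group on a variable that cannot support it.

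The mixed-group sentence follows one dated days 10-15, so that window is a natural reading, though it is not stated.

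Three further points are useful additions:

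- The results appear to date the initial value to postoperative days 1-2, when no weighing was planned.
- The protocol's study plan includes fat mass, water and dry matter, which could help separate fluid from tissue.
- Six kinds of operation were included and allocation to groups is not described, so between-group weight differences may be confounded.

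**Conclusion.** The concern holds. Given the documents' own definition, the energy-coverage claim in the results and in Conclusion 3 does not follow, whether or not a factor was added. This rests on no calculation and no outside source.

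The implied baseline of 2413.6 and fall of 163.6 kcal/day assume that 6.78% is relative to the group's own start. The 6.8% to 13.6% weight range assumes a 50-100% weight share and no added factor. The Welch results apply only if the printed means are end values.

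The damage is limited to the basal-metabolism component of Objective 3 and the comparative claim in Conclusion 3. Conclusion 1 and the nutritional-status component are not affected by this point.

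**What to change.** 1. Withdraw the energy-coverage inference from the results and from Conclusion 3.
2. Under Objective 3, report the calculated rate only as a descriptive estimate of requirement. Make a coverage statement only if delivered energy was recorded and can be set against requirement by group and day.
3. State the exact formula and any temperature or other factor. Give each group's baseline, when it was taken and which weight was used. Label 2500.1, 2350.0 and 2250.0 as initial or end values, and ± as SD or SE. State the day of the mixed-group result, the test behind p<0.03, and whether it is within or between groups.
4. Report baseline-adjusted between-group differences in weight and BMI with 95% CIs and numbers weighed at days 5, 10 and 15, as a nutritional-status result and not as a measure of coverage. Add the body-composition data if collected, and note the operation mix and undescribed allocation as limits.
5. Reconcile days 10-15 in the results with days 15-20 in Conclusion 3 for the enteral and parenteral groups. The last planned weighing is day 15.

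The cost is mostly wording and labelling, plus a small re-analysis of recorded weights. Day-15 weights may be incomplete. If delivered energy was not recorded, no coverage claim can be made, and one statement favouring mixed nutrition is lost.

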43-87% of patients with malignant neoplasms of various localizations have pronounced disturbances in body composition, which correlate with the prevalence of the tumor process and are aggravated during combined treatment. This is based on disturbances in protein, carbohydrate and fat metabolism caused by the systemic effect of the tumor on the body. Violation of nutritional status has a significant impact on the outcome and prognosis of the disease, inevitably increases the duration and cost of treatment, contributes to an increase in mortality and the number of complications, such as infection, slower wound repair, immunosuppression, hemocoagulation disorders, decreased concentrations of blood plasma proteins and a number of enzymes, metabolic disorders medications, decreased tolerance to surgical treatment, radiation and chemotherapy. BUT. Stadley showed that when depleted patients lost 20% of their initial body weight, mortality after surgery reached 33%, and in non-depleted patients -3.5%. According to B.R. Bistrian, G.L. Blakburn, with a 5% decrease in body weight during hospital stay, the length of stay increases by 2 times, and the frequency of complications increases by 3.3 times. J.L. Mullen and G.P. Buzby (1980) showed that impaired nutritional status in surgical patients leads to an increase in postoperative complications by 6 times, and mortality by 11 times, while timely administration of adequate nutritional therapy to such depleted patients reduces the number of postoperative complications by 2-fold. 3 times, and lethality - 7 times.

In this regard, the importance of accurately assessing the nutritional status of patients is obvious, which is the first step in treating and preventing further progression of malnutrition. A variety of methods are used to assess a patient's nutritional status. The use of enteral nutrition in the postoperative period contributes to the rapid elimination of intestinal paresis, early activation of intestinal motility, improved regeneration of the intestinal mucosa and activation of its absorption function.

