## **2. Data analysis and monitoring.**

Statistical processing of the obtained data will be carried out using the application package STATISTICA version 7.0, taking into account computational methods recommended for biology and medicine. Statistical research methods include: calculation of median and mode, standard deviation. To determine the reliability of the obtained indicators, Student's t-test will be used. Also calculate the pairwise correlation coefficient according to Pearson.

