### Scientific hypothesis

Complete and comprehensive nutritional support for patients operated on for malignant neoplasms of the hepatopancreatoduodenal zone, in the form of various approaches and methods of delivering nutrients to patients in the early postoperative period, allows to improve the functional activity of the gastrointestinal tract of patients, stabilize the level of carbohydrate, protein, basal metabolism, accelerate transfer to full enteral nutrition and reduce the length of stay in the intensive care unit and, ultimately, in the hospital.

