## **Methods of statistical data analysis**

All patients hospitalized for special treatment with a verified diagnosis of a malignant neoplasm were subjected to the study in the abdominal department of the KGP at the Regional Oncological Dispensary, Karaganda.

The quantitative and qualitative indicators obtained during the study were analyzed using descriptive and analytical statistics methods. For statistical processing of qualitative (diagnosis codes, dichotomous data) and quantitative variables: symptom intensity, severity, frequency of occurrence, we used the calculation of the median level (Me) with 25%-75% quartiles (Q25; Q75) and the calculation of the arithmetic mean (M) with error (m) and 95% confidence interval (95% CI), standard deviation (s). Quantitative variables were checked for normality of distribution using the Kolmogorov-Smirnov test, as well as the module of Skewness and Kurtosis for quantitative variables  $| \leq 2 |$ . Differences in the 3 groups of patients for quantitative variables corresponding to a normal distribution were identified using the Student's t test for unrelated groups, first for 3 or more groups, and then in pairs for each pair using the Student's t test. Differences for rank variables, or quantitative but not normally distributed for unrelated groups, were determined by the Kruskal-Wallis test or median test for 3 groups, and then pairwise or non-parametric Mann-Whitney test for each of the 3 pairs (groups 1 and 2, groups 1 and 3, groups 2 and 3), and for related groups (dynamic observations) by the Kendall test for 3 groups and then by the Wilcoxon test (Wilcoxon) for each of the 3 pairs (baseline, after 5 days and after 10 days).

Correlation was performed for quantitative variables according to Pearson and for rank variables according to Spearman. Statistical processing of the results was carried out using the Statistica program version 10.

**Results and discussion.** The nutritional status of patients in all three groups before surgery and during the 10-12 days of the postoperative period according to the methods of assessing nutritional status NRS, SGA and NRI was assessed as normal, moderate and severe malnutrition

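### ICU and hospital stay are compared as raw durations with no rule for deaths; if early deaths differ between arms, the arm with more of them gains an artificially shorter stay.

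*Combined protocol and SAP*

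**What the plan says.** Protocol section III, under *Methods and procedures*, lists among its additional measures "the length of patients' stay in the ICU, the readmission of patients to the ICU and the duration of the postoperative bed-day", and also "the duration of postoperative gastostasis, the timing of the onset of intestinal motility, the appearance of stool, the return to a normal diet". The report's *Clinical research program* repeats the list. The *Scientific hypothesis* in the report says support will "reduce the length of stay in the intensive care unit and, ultimately, in the hospital".

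The comparative methods are generic:

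- Protocol, *Data analysis and monitoring*: "To determine the reliability of the obtained indicators, Student's t-test will be used".
- Report, *Methods of statistical data analysis*, normally distributed variables: differences "were identified using the Student's t test for unrelated groups, first for 3 or more groups", then in pairs.
- Same section, rank or non-normal variables: differences "were determined by the Kruskal-Wallis test or median test for 3 groups", then pairwise Mann-Whitney.

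Neither the protocol nor the report lists death as a separate outcome, gives deaths by arm, defines discharge as discharge alive, or names a censoring, competing-risk or worst-rank rule. Mortality appears only in the Introduction, which says that in depleted patients "mortality after surgery reached 33%, and in non-depleted patients -3.5" per cent (the dash is punctuation, not a minus sign).

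**The concern.** A length of stay ends either by discharge or by death. On raw values a patient who dies on day 5 has a 5-day stay, which ranks better than a survivor discharged on day 15. That patient also cannot be readmitted to the ICU. If one arm has more early deaths, both a t-test and a rank test move in its favour on a measure that the hypothesis counts as a benefit.

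Deaths are plausible in this setting. The operations include hemihepatectomy and gastro-pancreatoduodenal resection, with care in an intensive care unit. At the lowest mortality the Introduction cites, the chance of at least one death among 91 patients is 1 − (1 − 0.035)^91 = 96%.

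**Working it through.** The documents give no design figure, stay data or death count to reproduce. The check therefore asks how large the distortion could be on inputs as close to this trial as the documents allow.

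**Inputs from the documents.** Arm sizes are 31 (enteral), 30 (parenteral) and 30 (mixed). Patients with normal SGA status before surgery number 24, 19 and 17 (report, *Results and discussion*). Background mortality is 33% in depleted and 3.5% in non-depleted patients.

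**Assumptions.** Every patient who is not SGA-normal carries 33%, and all others 3.5%. This is upper-end, because the 33% belongs to patients who had lost 20% of body weight. Hospital stay in survivors is identical across arms, log-normal with median 15 days and log-SD 0.35. Deaths fall on days 3 to 7. Tests are two-sided at 0.05 (the documents state no alpha), so the nominal rate in one direction is 2.5%.

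**Step 1: expected mortality by arm** = (not normal × 0.33 + normal × 0.035) / n

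| Arm | Not normal | Normal | Expected mortality |
|---|---|---|---|
| Enteral | 7 | 24 | (2.31 + 0.84) / 31 = 10.2% |
| Parenteral | 11 | 19 | (3.63 + 0.665) / 30 = 14.3% |
| Mixed | 13 | 17 | (4.29 + 0.595) / 30 = 16.3% |

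The largest gap, mixed against enteral, is 6.1 percentage points.

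**Step 2: shift in mean stay** ≈ (difference in death proportion) × (mean survivor stay − mean day of death). Mean survivor stay is 15 × exp(0.35²/2) = 15.9 days and the mean day of death is 5. The shift is 0.061 × (15.9 − 5) ≈ 0.67 day, shorter in the arm with more deaths. Simulation gives 0.6 to 0.7 day.

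The shift grows with survivor stay. With a mean day of death of 4.5, survivor means of 12, 18 and 24 days give 0.061 × 7.5 = 0.46, 0.061 × 13.5 = 0.82 and 0.061 × 19.5 = 1.19 days.

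**Step 3: false favour.** In simulated trials at 10.2% v 16.3%, with no true difference in survivors, the Mann-Whitney test declares the higher-mortality arm significantly shorter in about 5 to 6%, roughly double the nominal 2.5%. With equal mortality the rate is about 2.4%, so it is the mortality gap that causes the excess. With deaths ranked as the worst value the rate falls to about 1%.

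**Step 4: larger gaps, for scale only.** Against 3.5% in the other arm, in the same log-normal model:

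| Mortality in the worse arm | Shift in mean stay | False favour (Mann-Whitney) |
|---|---|---|
| 10% | 0.7 day | 6 to 7% |
| 20% | 1.8 days | 18 to 19% |
| 33% | 3.2 to 3.3 days | 49 to 51% |

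**Scope of the figures.** They illustrate hospital stay. The Step 2 formula shortens a stay only when death comes before a survivor would typically have left. For ICU stay the documents give no lengths, so no size can be attached.

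**The case against.** The strongest reply is that the plan is silent on deaths rather than instructing anyone to pool them. The report compares no stay or recovery time and mentions no death. The protocol (section IV, *Potential risk*) removes a patient whose chronic disease flares up, so some deteriorating patients may leave the data altogether, which is a different problem. Stay is an additional measure, absent from the three objectives and placed last in the hypothesis, and no conclusion rests on it. All of this stands, and it makes the point conditional. It does not fill the gap, because the tests named, applied to the durations listed, give no separate treatment to a death.

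Three stronger readings are tempting and are not supported:

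- A reader might carry 33% v 3.5% across to two arms and expect a false result in about half of trials. Those figures describe different kinds of patient, not arms. The reported SGA mix gives a gap of about 6 points even on the upper-end assumption. A treatment effect on mortality could widen it, but the documents give no figure for one.
- A reader might infer that every recovery time is biased the same way. A patient who dies before motility, stool or normal diet has no value for that outcome. The direction depends on whether the time is cut at death or the patient is dropped, which is not stated. The arm can appear faster, but need not.
- A reader might infer that deaths explain the report's preference for mixed nutrition. That conclusion rests on nutritional scales and basal metabolism, not on stay.

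Nor do the report's counts show that everyone survived. The parenteral arm on days 10-12 totals 17 + 14 = 31 against n = 30, and 26 patients given as 81.6% implies a denominator of about 32. They settle nothing either way.

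**Conclusion.** The concern holds as a conditional one. ICU stay and postoperative bed-days are to be compared as raw durations with deaths not separated, so an arm with more early deaths would gain an artificially shorter stay. On the baseline SGA mix and the background mortality figures, taken as an upper-end assumption, the distortion in hospital stay is about 0.6 to 0.7 day, with about 5 to 6% false favour against 2.5% nominal. In that illustration it favours the mixed arm. The size rests on assumed survivor stay, timing of death and alpha. No reported conclusion is shown to be wrong. It is still worth correcting, because the protocol intends a dissertation, publications and conference reports, where stay comparisons could yet appear.

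**What to change.** In the protocol's *Methods and procedures* and the report's *Clinical research program* and *Methods of statistical data analysis*:

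1. Define the stay outcomes as time to ICU discharge alive and time to hospital discharge alive, and say whether ICU readmission days are counted.
2. Rank in-hospital death as the worst value and use the rank tests already named (Kruskal-Wallis, then Mann-Whitney) for these outcomes whatever their distribution, since a t-test cannot carry a worst rank. Alternatively, treat death as a competing event and compare cumulative incidence.
3. Treat death before motility, stool or normal diet in the same way.
4. Print deaths by arm beside each of these outcomes and beside ICU readmission. If nobody died, one sentence saying so resolves the point.
5. Base any statement on stay on this analysis.

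The cost is a re-analysis with no new patients. The result becomes a median or a cumulative incidence instead of a mean number of days. The documents do not show that death dates were recorded, so these may have to be taken from the medical records.
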